#### **Actions required when potential Hy’s law criteria are met before and after starting study treatment**

This section is applicable to patients who meet PHL criteria on study treatment (including the 30 day follow-up period post discontinuation of study treatment) having previously met PHL criteria at a study visit prior to starting study treatment.

At the first on study treatment occurrence of PHL criteria being met the Investigator will:

- Determine if there has been a significant change in the patients’ condition compared with the last visit where PHL criteria were met
  - If there is no significant change no action is required

- If there is a significant change notify the AstraZeneca representative, who will inform the central Study Team, then follow the subsequent process described in Potential Hy's law criteria met of this Appendix.

A 'significant' change in the patient's condition refers to a subsequent clinically relevant change in any of the individual liver biochemistry parameters (ALT, AST or total bilirubin) in isolation or in combination, or a clinically relevant change in associated symptoms such as fatigue, vomiting, rash, right upper quadrant pain, jaundice, eosinophilia. The determination of whether there has been a significant change will be at the discretion of the Investigator; this may be in consultation with the Study Physician if there is any uncertainty.

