##### **Potential Hy's Law Criteria met**

If the patient does meet PHL criteria the Investigator will:

- Determine whether PHL criteria were met at any study visit prior to starting study treatment in the presence of liver metastases
- Notify the AstraZeneca representative who will then inform the central Study Team

The Study Physician contacts the Investigator, to provide guidance, discuss and agree an approach for the study patients' follow-up and the continuous review of data. Subsequent to this contact the Investigator will:

- Monitor the patient until liver biochemistry parameters and appropriate clinical symptoms and signs return to normal or baseline levels, or as long as medically indicated
- Investigate the etiology of the event and perform diagnostic investigations as discussed with the Study Physician
- If at any time (in consultation with the Study Physician) the PHL case meets serious criteria, report it as an SAE using standard reporting procedures

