#### **Review and Assessment of potential Hy's law cases**

The instructions in this Section should be followed for all cases where PHL criteria are met.

No later than 3 weeks after the biochemistry abnormality was initially detected, the Study Physician contacts the Investigator in order to review available data and agree on whether there is an alternative explanation for meeting PHL criteria other than DILI caused by the IMP. The AstraZeneca Medical Science Director and Global Safety Physician will also be involved in this review together with other subject matter experts as appropriate.

According to the outcome of the review and assessment, the Investigator will follow the instructions below.

If there **is** an agreed alternative explanation for the ALT or AST and TBL elevations, a determination of whether the alternative explanation is an AE will be made and subsequently whether the AE meets the criteria for a SAE:

- If the alternative explanation is **not** an AE, record the alternative explanation on the appropriate CRF
- If the alternative explanation is an AE/SAE, record the AE /SAE in the CRF accordingly and follow the AZ standard processes

If it is agreed that there is **no** explanation that would explain the ALT or AST and TBL elevations other than the IMP:

- Report an SAE (report term ‘Hy’s Law’) according to AstraZeneca standard processes.
  - The ‘Medically Important’ serious criterion should be used if no other serious criteria apply
  - As there is no alternative explanation for the HL case, a causality assessment of ‘related’ should be assigned.

If, there is an unavoidable delay, of over 3 weeks, in obtaining the information necessary to assess whether or not the case meets the criteria for HL, then it is assumed that there is no alternative explanation until such time as an informed decision can be made:

- Report an SAE (report term ‘Potential Hy’s Law’) applying serious criteria and causality assessment as per above
- Continue follow-up and review according to agreed plan. Once the necessary supplementary information is obtained, repeat the review and assessment to determine whether HL criteria are met. Update the SAE report according to the outcome of the review.

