#### **Actions required for repeat episodes of potential Hy's law**

This section is applicable when a patient meets PHL criteria on study treatment (including the 30-day follow-up period) and has already met PHL criteria at a previous on study treatment visit.

The requirement to conduct follow-up, review and assessment of a repeat occurrence(s) of PHL is based on the nature of the alternative cause identified for the previous occurrence.

The investigator should determine the cause for the previous occurrence of PHL criteria being met and answer the following question:

- Was the alternative cause for the previous occurrence of PHL criteria being met chronic or progressing malignant disease or did the patient meet PHL criteria prior to starting study treatment and at their first on study treatment visit as described in Actions Required When Potential Hy's Law Criteria are Met Before and After Starting the Study.

If No: Follow the process described in Potential Hy's Law Criteria Met of this Appendix.

If Yes: Determine if there has been a significant change in the patient's condition compared with when PHL criteria were previously met

- If there is no significant change no action is required
- If there is a significant change follow the process described in Potential Hy's Law Criteria Met of this Appendix.

A 'significant' change in the patient's condition refers to a subsequent clinically relevant change in any of the individual liver biochemistry parameters (ALT, AST or total bilirubin) in isolation or in combination, or a clinically relevant change in associated symptoms, such as fatigue, vomiting, rash, right upper quadrant pain, jaundice, eosinophilia. The determination of whether there has been a significant change will be at the discretion of the Investigator; this may be in consultation with the Study Physician if there is any uncertainty.

Clinical Study Protocol Appendix C  
Drug Substance AZD9291  
Study Code D5160C00022  
Version 3  
Date 20 October 2016

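### Appendix C's no-action route for potential Hy's law omits the liver-metastases condition in the check that comes before it

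*Protocol*

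**What the plan says.** Four sections of Protocol Appendix C matter here.

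- *Potential Hy's Law Criteria met* sets the general process. Its first instruction is: "Determine whether PHL criteria were met at any study visit prior to starting study treatment in the presence of liver metastases". The investigator then notifies the sponsor's representative, monitors the patient and investigates the cause with the Study Physician.
- *Review and Assessment of potential Hy's law cases* opens with: "The instructions in this Section should be followed for all cases where PHL criteria are met". Within three weeks, the investigator and sponsor physicians agree whether anything other than the study drug explains the values. If the information is delayed beyond that, no alternative explanation is assumed and an SAE is reported.
- *Actions required when potential Hy's law criteria are met before and after starting study treatment* covers patients who meet the criteria on treatment, "having previously met PHL criteria at a study visit prior to starting study treatment". The instruction begins "At the first on study treatment occurrence of PHL criteria being met the Investigator will" and asks for a judgement on whether the patient's condition has changed significantly "compared with the last visit where PHL criteria were met". The outcome is: "If there is no significant change no action is required". If there is a significant change, the sponsor is notified and the general process follows. The judgement is the investigator's, and consulting the Study Physician is optional.
- *Actions required for repeat episodes of potential Hy's law* opens a no-action route in two situations. One is that the previous episode was put down to chronic or progressing malignant disease. The other is phrased as a question: "did the patient meet PHL criteria prior to starting study treatment and at their first on study treatment visit". Change is again judged by the investigator, "compared with when PHL criteria were previously met".

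**The concern.** A no-action route is reasonable for a patient whose liver values were already abnormal because of liver metastases and have stayed much as they were. A known cause stands in for the causality review. The general process reflects this, because it asks about pre-treatment abnormality only where liver metastases were present.

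The section that uses the answer does not carry that condition. A patient whose pre-treatment elevation had some other cause, such as a previous drug, hepatitis or biliary disease, falls inside the exception as well. For that patient there is no metastatic explanation to rely on. If the thresholds are met again on treatment, drug-induced liver injury remains possible, and the joint review is the step designed to settle it. The stake is that the sponsor notification and the joint review can both be skipped on one investigator's judgement that nothing significant has changed.

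**Working it through.** No arithmetic applies, so the check sets the sections side by side.

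| Appendix C section | Patients covered | Liver metastases required? | Identified cause required? | Result if no significant change |
|---|---|---|---|---|
| Potential Hy's Law Criteria met (the check) | Criteria met before treatment | Yes | No | None stated; notification is unconditional |
| Before and after starting treatment | Criteria met before treatment and again on treatment | No | No | No action |
| Repeat episodes, first branch | Previous episode had an alternative cause | No | Yes: chronic or progressing malignant disease | No action |
| Repeat episodes, second branch | Criteria met before treatment and at the first on-treatment visit | No | No | No action |

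**Step 1: compare the groups.** Let A be the patients who reached the laboratory thresholds at a pre-treatment study visit, and L those who had liver metastases at that time. The check picks out A and L together. The before-and-after section covers all of A. The second group contains the first, and the difference is A without L. (Appendix C's PHL definition runs only from the start of study medication, so criteria met before treatment has to be read as the same laboratory thresholds reached earlier.)

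**Step 2: are the two sections linked?** The check gives no cross-reference, so the link is inferred. The inference is sound. The before-and-after section is where a pre-treatment finding is acted on, it refers back to the general process, and the repeat-episode section reaches such findings only by citing it. Within Appendix C, liver metastases are named only in the check.

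**Step 3: follow a patient in A without L to a first on-treatment episode.** The thresholds are met and the investigator sees no significant change, so no action is required. The significant-change arm of that section contains its own instruction to notify the sponsor. This implies that no notification is made in the other arm, so the joint review is not reached either.

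**Step 4: follow the same patient to a second on-treatment episode.** The repeat-episode section says its handling depends on what kind of alternative cause was identified last time. The first branch respects that principle. The second branch admits the patient on history alone. If the first episode took the no-action route, no cause was ever agreed, so a second episode can also pass without review. One limit applies: this branch speaks of the first on-treatment visit, whereas the section it cites speaks of the first on-treatment occurrence. Taken literally, it reaches fewer patients.

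**Step 5: can the extra group contain anyone?** Protocol section 3.1, criterion 6, asks for adequate organ function but sets no AST, ALT or bilirubin limit. Section 3.2, criterion 3, excludes hepatic impairment only where the investigator thinks it alters the risk/benefit balance, and it admits patients on oral suppressive therapy for hepatitis B or C. The group is therefore small but not empty by rule.

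**Step 6: what still operates?** The SAE definition and reporting duties (Protocol sections 6.2, 6.2.2 and 6.3) and the dose-interruption rule for drug-associated toxicity (section 6.6) are untouched. SAP section 3.2.3 summarises patients with potential Hy's law criteria. SAP Addendum section 4.1.3 cross-tabulates and lists them without exempting this group.

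**The case against.** The strongest case against the point is that the extra group is close to empty. A patient without liver metastases would need both transaminase and bilirubin at threshold before treatment, still be judged eligible, reach the thresholds again on drug, and show no clinically relevant change in any parameter or symptom. Section 3 of the Protocol allows no exceptions to eligibility, and metastatic disease is the likeliest reason for such values in an enrolled patient. This stands as an argument about size. It does not close the gap, because the eligibility wording rests on judgement rather than a limit.

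The second argument is that other safeguards exist. They do, and they limit the consequence. However, the SAP outputs are aggregate and come later, the SAE and dosing rules depend on the investigator's own assessment, and none of them replaces prompt notification and joint review.

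A reader might also infer a larger defect from the comparator: that a patient who recovers and relapses on drug escapes review because only the earlier PHL visit is named. With assumed values, ALT 4xULN and bilirubin 2.5xULN at screening, normal at week 6, and back to 4x and 2.5x at week 12 would show no difference from screening. The text does not support going that far. Both sections define a significant change as a later, clinically relevant change in any one of ALT, AST or total bilirubin, or in associated symptoms. Normalisation followed by recurrence most naturally falls within that definition. The check sets no comparator either, so this is not a mismatch between the two sections.

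**Conclusion.** The point holds for the missing liver-metastases condition. As written, a patient without liver metastases who met the criteria before and on treatment, with no significant change in the investigator's view, can bypass sponsor notification and the joint causality review. The second branch for repeat episodes extends this without requiring an identified cause.

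The size is small. The documents give no rate of pre-treatment values at these thresholds, so no number of patients can be stated. No planned analysis changes. The conclusion rests on two assumptions: that the before-and-after section is meant to use the answer to the check, and that investigators follow the text as written.

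Two further readings should be resisted. A reader might infer that Appendix C contradicts itself, because the review section claims every PHL case. The later sections have their own headings and stated scope, so they read as specific exceptions to a general rule. A reader might also infer that SAE reporting is switched off. It is not, because the general duties in Protocol section 6 continue to apply. Leaving significance to the investigator is a design choice and not part of the defect.

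Rating: minor, a cheap patient-safety improvement.

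**What to change.** 1. In *Actions required when potential Hy's law criteria are met before and after starting study treatment*, limit the section to patients who had liver metastases when the pre-treatment criteria were met.
2. In *Actions required for repeat episodes of potential Hy's law*, apply the same limit to the second branch of the question.
3. State that all other patients with pre-treatment criteria follow the general process and the joint review.

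Two optional clarifications could go in at the same time. One is to say that normalisation followed by recurrence counts as a significant change. The other is to add an exception clause to the opening sentence of the review section. Neither is needed for the main fix.

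The cost is a short wording change in Appendix C and a few extra notifications and reviews. No new data item is needed, because the existing check already asks about liver metastases and the investigator already reviews laboratory reports from all previous visits.

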#### **Actions required for repeat episodes of potential Hy's law**

This section is applicable when a patient meets PHL criteria on study treatment (including the 30-day follow-up period) and has already met PHL criteria at a previous on study treatment visit.

The requirement to conduct follow-up, review and assessment of a repeat occurrence(s) of PHL is based on the nature of the alternative cause identified for the previous occurrence.

The investigator should determine the cause for the previous occurrence of PHL criteria being met and answer the following question:

- Was the alternative cause for the previous occurrence of PHL criteria being met chronic or progressing malignant disease or did the patient meet PHL criteria prior to starting study treatment and at their first on study treatment visit as described in Actions Required When Potential Hy's Law Criteria are Met Before and After Starting the Study.

If No: Follow the process described in Potential Hy's Law Criteria Met of this Appendix.

If Yes: Determine if there has been a significant change in the patient's condition compared with when PHL criteria were previously met

- If there is no significant change no action is required
- If there is a significant change follow the process described in Potential Hy's Law Criteria Met of this Appendix.

A 'significant' change in the patient's condition refers to a subsequent clinically relevant change in any of the individual liver biochemistry parameters (ALT, AST or total bilirubin) in isolation or in combination, or a clinically relevant change in associated symptoms, such as fatigue, vomiting, rash, right upper quadrant pain, jaundice, eosinophilia. The determination of whether there has been a significant change will be at the discretion of the Investigator; this may be in consultation with the Study Physician if there is any uncertainty.

Clinical Study Protocol Appendix C  
Drug Substance AZD9291  
Study Code D5160C00022  
Version 3  
Date 20 October 2016

## VERSION HISTORY

**Table 4 (footnote c)** was amended:

A 30 day post last dose follow up contact (**visit or by telephone**) should be made with the subject **to collect new SAEs and AESI and to follow up on any ongoing SAEs and AESI-** to clarify the type of contact.

**Section 5 Study Measures:** was modified to introduce the collection of imaging assessments (CT scans or MRI) from baseline and following visits from a subset of patients where a T790M positive mutation was identified via the **cobas®** EGFR Mutation Test performed on a plasma or tissue specimen. CCI

The collection of imaging assessments (CT scans or MRI) from baseline and following visits has also been added for patients where a T790M positive mutation was identified via other molecular testing methods. - was also added.

**Central reading of imaging assessments** was added in section 5

All imaging assessments from a selected subset of patients (where available and Informed Consent is obtained), including unscheduled visit scans, should be collected and sent to an AstraZeneca appointed Clinical Research Organisation to enable independent central analyses. The central imaging review is required only for this selected subset of patients where a selected T790M positive mutation test was performed on a plasma or tissue specimen. The baseline scan should ideally be performed within 28 days of the start of treatment. The results of this independent review will not be communicated to investigators. The purpose of this review is to assess tumour response according to RECIST 1.1 in order to evaluate the objective response rate in these subsets of patients with various methods of T790M molecular testing.

Further details will be provided in the Statistical Analysis Plan.

**Section 6.4 Overdose** was modified to be in line with the AstraZeneca protocol template and SOP.

There is no definition of what constitutes an overdose. In the Phase I study, 355 patients with advanced NSCLC were administered AZD9291 at single and multiple oral doses ranging from

20 mg to 240 mg daily (as of data cut-off date 02 December 2014). All doses were well tolerated. Experiences of excessive doses (i.e. in excess of the optimal 80 mg indicated dose) in this study did not show any DLTs or acute toxicities.

There is no known antidote. Investigators are advised that any patient, who receives a higher dose than intended should be monitored closely, managed with appropriate supportive care, and followed up expectantly.

Such overdose must be recorded in the CRF ~~if the overdose is associated with an SAE.~~

**Section 11.4 Informed consent** was modified and the following paragraph was added:

Ensure that the Addendum to the ICF is signed and dated for the subset of patients tested for a T790M positive mutation via the **cobas®** EGFR Mutation Test (or any other molecular testing methods if relevant) before any imaging assessments are collected.

#### **Version 2.0, 23 June 2016**

**Is applicable to all participating countries.**

Changes to the protocol are summarised below.

#### **Section of protocol affected:**

In PROTOCOL SYNOPSIS-

#### **Study site(s) and number of patients planned.**

The number of patients enrolled is reduced in Europe (from 1500 to 600) due to lower enrolment than initially planned. The total number of patients is more defined and with the participation of China, the total number of patients expected would be approximately 3500 by the time the study ends in Q4 2020.

#### **Duration of IP administration**

Removal of the patient registry after national reimbursement. This means that the data collection for ASTRIS stops at the last patient last visit.

#### **Statistical methods**

Addition of the Time to Treatment Discontinuation (TTD) in the secondary endpoints.

In the body of the protocol:

#### **2. Study Objective**

Clarification of primary and secondary objectives: **The primary efficacy outcome is OS,**

**with secondary efficacy outcomes including investigator assessed response rate, investigator assessed PFS and Time to Treatment Discontinuation (TTD).**

### **3.2 Exclusion criteria**

Clarification of exclusion criteria # 3 (with \*)

Any evidence of severe or uncontrolled systemic diseases, including uncontrolled hypertension, active bleeding diatheses, active infection\* including hepatitis B, hepatitis C and human immunodeficiency virus, or significantly impaired bone marrow reserve or organ function, including hepatic and renal impairment, which in the investigator's opinion would significantly alter the risk/benefit balance.

**\* active infection will include any patients receiving intravenous treatment for any infection and patients with hepatitis B or C surface antigen (+) – Patients receiving oral antiviral suppressive therapy for hepatitis B or C will be permitted to enrol in the study**

